#### 4.1.2 Method of assigning patients to treatment groups

When a patient is qualified for entry into the randomised treatment period, treatment assignment will be by means of a third-party phone/web-based randomisation on Visit 2. This will involve the use of an Interactive Response Technology (IRT) system which will implement a randomisation scheme generated using a validated randomisation software by Boehringer Ingelheim.

Refer to [Section 4.1.6](#) for details on packaging and labelling.

Note that the Respimat® treatment box number assigned to the patient by the IRT is different from the study patient number assigned by the Remote Data capture (RDC) system upon signing informed consent.

Details on the IRT system are provided in the ISF.

#### 4.1.3 Selection of doses in the trial

The clinical trials conducted during the Phase III programme for tiotropium + olodaterol FDC 5/5 µg have shown that this dose is a safe, well tolerated and efficacious combination therapy. The observed incremental bronchodilator response for the combination compared to the individual components translated into benefits that were meaningful to the patient, with improvements in several patient centred outcomes. An additional dose of tiotropium + olodaterol FDC has been studied during the Phase III programme, consisting of 2.5 µg tiotropium and 5 µg olodaterol. In the pivotal trials, a consistent difference in favour of tiotropium + olodaterol FDC 5/5 µg compared to tiotropium + olodaterol FDC 2.5/5 µg was demonstrated over the 52 week treatment period across various measures of lung function and patient-reported outcomes. Tiotropium + olodaterol FDC 5/5 µg demonstrated statistically significant and clinically relevant benefit over the individual components in all primary and secondary endpoints. On the other hand, the lung function improvement for tiotropium + olodaterol FDC 2.5/5 µg was more modest and a statistically significant benefit was not demonstrated in the pre-specified symptomatic primary endpoint, SGRQ total score. Based on these observation, the tiotropium + olodaterol FDC 5/5 µg has been submitted for regulatory approval and is therefore considered to be the most appropriate dose to be studied in this trial.

Tiotropium 5µg (2.5 µg / per actuation) inhalation solution Respimat® has been approved in more than 80 countries worldwide including Europe and Japan as an antimuscarinic bronchodilator with a once daily posology [REDACTED]. Therefore the marketed dose of tiotropium Respimat is deemed an adequate comparator for the study.

#### 4.1.4 Drug assignment and administration of doses for each patient

Trial medication will be dispensed to the patient by the investigator/pharmacist. At Visit 2 eligible patients will be randomized to one of two double-blinded treatment arms (1:1 ratio) by the IRT. At subsequent clinic visits (every 3 months), the IRT will assign Respimat® treatment boxes to each patient and each Respimat® treatment box will have a unique number with 6 digits.

One of these Respimat® treatment boxes is a reserve Respimat® inhaler. This reserve kit allows the patient the flexibility of not having to return to the clinic immediately to replace a lost or malfunctioning Respimat® inhaler. In the event that a patient may need additional extra Respimat® inhalers and cartridges due to rescheduled visits, inhaler loss or malfunction, these will be supplied on an 'on demand' basis. Dispensing of these extra Respimat® inhalers will also be managed via the IRT.

Site personnel will enter all medication numbers dispensed to each patient in the Medication Record page of the electronic case report form (eCRF).

#### 4.1.4.1 Priming of the Respimat® inhaler

[figure not shown]
Each newly assembled Respimat® inhaler has to be primed when appropriate. The Respimat® inhaler should be primed by actuating it until an aerosol is visible plus three additional actuations. All priming actuations should be directed to the ground.

Once assembled, the shelf-life of the Respimat® inhaler with study medication or training medication (placebo) is 3 months. Therefore it is important to ALWAYS enter the date of the cartridge insertion on the medication label of the Respimat® inhaler immediately after the cartridge is inserted.

For detailed priming instructions please refer to the Respimat® inhaler handling instructions in [Appendix 10.1](#)

#### 4.1.4.2 Study medication administration

For the patient's sake of convenience regarding the trial drug administration, the clinic visit must be scheduled in the morning. During the treatment phase the patient will be instructed to withhold the morning dose of the trial medication in current use prior to come to visits 3, 4 and 5 to avoid overdosing.

The last administration of the study medication will be taken at visit 6 (EoT) from the Respimat® inhaler that is in current use since no new Respimat® treatment box will be assigned.

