## FLOW CHART

Study periods	Screening*	Randomised 52-week treatment period										Follow-up****	
		V2		V3		V4		V5		V6 EoT 	V6a 		
Study visits** (V) and phone call ()***	V1												
Study day from Visit 2 (Days)	-1 to -7	Day1	D45 ±7	D90 ±7	D135 ±7	D180 ±7	D225 ±7	D270 ±7	D315 ±7	D360 +7	+ 1 day from V6/EoT	+21 days after V6/EoT (+7)	
Informed Consent	X 												
Demographics	X												
Cardiovascular risk-factors	X												
Concomitant Diagnosis	X 2												
Physical examination	X									X		X 	
Laboratory tests	X 									X 		X 	
Smoking status	X									X			
12-lead ECG	X												
Review of in-/exclusion criteria	X	X											
Serum pregnancy test 	X									X			
Urine pregnancy test		X		X		X		X				X	
Screening call (IRT)	X												
Inhalation device trainings 	X 10a	X 10b		X 10c		X 10c		X 10c					
Rescue medication dispensation	X 	X		X		X		X		X			
Medication restriction review	X 	X 											
Trial patient's card	X												
Randomisation call (IRT)		X											
Administration of trial drugs in clinic		X		X		X		X					
Last administration of trial drugs in clinic										X			
Assign trial drugs (IRT)		X		X		X		X					
Dispense Patient's reminder card		X		X		X		X		X			
COPD exacerbation interview		X	X	X	X	X	X	X	X	X		X	
Collect trial drugs/accountability				X		X		X		X			
Collect rescue medication/accountability				X		X		X		X		X	
Compliance check				X		X		X		X			
Discontinuation assessment Vital status collection.						X 						X 	
Discontinuation assessment COPD exacerbation collection			X 	X 	X 	X 	X 	X 	X 	X 			
Trial drug termination call (IRT)										X			
Adverse events	X	X	X	X	X	X	X	X	X	X	X	X	
Concomitant medication	X	X	X	X	X	X	X	X	X	X	X	X	
Conclusion of patient participation												X	
Trial Completion												X	

Proprietary confidential information.

© 2015 Boehringer Ingelheim International GmbH or one or more of its affiliated companies. All rights reserved.

This document may not - in full or in part - be passed on, reproduced, published or otherwise used without prior written permission.

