## STUDY PERIODS

- \* The visit interval (Visit 1-2) may be extended beyond 7 days for administrative reasons (1 additional week) or to allow for recovery from respiratory infections (4 weeks after recovery from the infection).
  - \*\* Clinic visits: every 3 months from visit 2
  - \*\*\* Phone calls: between clinic visits, every 6 weeks
  - \*\*\*\* Conclusion of patient participation also needs to be completed if the patient withdraws prematurely following randomisation.
1. Informed Consent: all patients must sign an informed consent consistent with ICH-GCP guidelines prior to any study related activities which includes medication washout and restrictions. A preliminary check of in-/exclusion criteria with a particular focus on COPD exacerbation status within the previous year is recommended to avoid unnecessary study procedures in non-eligible patients.
  2. FEV1/FVC: historical data from spirometry measurements within the past 3 months either at the site or at a referral site will be used. Spirometry results for COPD severity staging need to be in the patient file on site prior to randomisation. For patients participating in the spirometry sub-study, historical data will not be used for inclusion.
  3. Medication restriction review: Refer to [Table 4.2.2.1: 1](#) (Permitted Medications and Medication Restrictions)
  4. Visit 6/EoT procedures are to be completed by all patients at the time of study drug discontinuation. For patients who discontinue early, the Visit 6/EoT visit should be performed instead of the scheduled trial visit at time of discontinuation. Please complete directly Visit6/EoT eCRF pages.

[figure not shown]
6. Physical examination, vital signs and laboratory results: to be performed only if relevant findings at Visit 6 (or last treatment visit in case of premature discontinuation). Please refer to [section 5.2.3.1](#) (Laboratory tests) and [section 5.2.3.2](#) (Physical examination)
7. For prematurely discontinued patients: Vital status and COPD exacerbation status collection: Please refer to [section 3.3.4.1](#)
8. Rescue medication: to be dispensed to all patients. Please refer to [section 4.2.1.1](#)
9. Laboratory testing: fasted condition is not required
10. Inhalation device trainings: please refer to [section 4.1.4.3](#)
  - 10a: visit1, training session with the Respimat® inhaler training medication (placebo)
  - 10b: visit 2, training session with the new assigned Respimat® treatment box

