## 4. TREATMENTS

### 4.1 TREATMENTS TO BE ADMINISTERED

The study medication below will be supplied by Boehringer Ingelheim Pharma GmbH & Co.KG.

Patients will be randomized (1:1) to one of the following treatments:

- Tiotropium + olodaterol FDC (2.5 µg / 2.5 µg per actuation) inhalation solution
- Tiotropium (2.5 µg / per actuation) inhalation solution.

The patients inhale two puffs from the Respimat® inhaler, once a day, in the morning.

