### **Study medication administration at home**

Each morning, oral inhalation of two puffs on the study medication from the assigned Respimat® inhaler will be self-administered by the patient. Patients should be encouraged to take their study medication at approximately the same time in the morning (morning dose window until noon). If a patient misses the daily dose he/she should take the next dose the day after. The patient must assemble and prime the Respimat® inhaler at home once the current used Respimat® inhaler is empty and the device is locked.

The patient will be asked to record any missed dose of study medication in a patient's reminder card.

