### Daily use of your RESPIMAT® inhaler

**You will need to use this inhaler only ONCE A DAY.  
Each time you use it take TWO PUFFS.**

 
I
	
I Hold the RESPIMAT® inhaler upright, with the grey cap (A) closed, to avoid accidental release of dose. Turn the base (G) in the direction of the red arrows on the label until it clicks (half a turn).

 
II
	
II Open the grey cap (A) until it snaps fully open. Breathe out slowly and fully, and then close your lips around the end of the mouthpiece without covering the air vents (C). Point your RESPIMAT® inhaler to the back of your throat. While taking in a slow, deep breath through your mouth, press the dose release button (D) and continue to breathe in slowly for as long as you can. Hold your breath for 10 seconds or for as long as comfortable.
 
III Repeat steps I and II so that you get the full dose.
 
You will need to use this inhaler only ONCE A DAY.
 
Close the grey cap until you use your RESPIMAT® inhaler again.
 
If the RESPIMAT® inhaler has not been used for more than 3 days release one puff towards the ground. If the RESPIMAT® inhaler has not been used for more than 21 days repeat steps 4 to 6 until a cloud is visible. Then repeat steps 4 to 6 three more times.

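### The instruction to skip the home dose before clinic dosing names Visits 3, 4 and 5 but leaves out Visit 6/EoT, where trial drug is also taken in clinic

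*Protocol*

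**What the plan says.** Protocol section 4.1.4.2 has clinic visits scheduled in the morning and instructs the patient to "withhold the morning dose of the trial medication in current use prior to come to visits 3, 4 and 5 to avoid overdosing". Its next paragraph turns to the final visit: "The last administration of the study medication will be taken at visit 6 (EoT) from the" inhaler the patient is already using, because no new one is assigned. The flow chart has a separate row, "Last administration of trial drugs in clinic", marked at Visit 6/EoT, and section 6.2.3.1 lists the same dose among the Visit 6 procedures.

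The home-dosing text under section 4.1.4.2 reads "Each morning, oral inhalation of two puffs on the study medication from the assigned" inhaler, with no exception for the Visit 6 morning. Section 4.1 sets the regimen as two puffs from the "inhaler, once a day, in the morning", and the patient leaflet in Appendix 10.1 says "You will need to use this inhaler only ONCE A DAY".

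Flow chart footnote 4 adds that "Visit 6/EoT procedures are to be completed by all patients at the time of study drug discontinuation", so the same visit applies to patients who stop early.

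**The concern.** The withhold instruction exists for one stated reason, to prevent overdosing on days when drug is given in clinic. Visit 6/EoT is such a day, and the instruction does not mention it. A patient who follows the home rule that morning and then takes the supervised dose receives twice the daily amount. Naming three visits out of four may also suggest to sites that the fourth is deliberately exempt.

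What is at stake is dosing safety on a single day. It is not the validity of the efficacy comparison.

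**Working it through.** The plan states no figure to reproduce. The check sets the dosing instructions side by side and adds up puffs.

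**Visits with a clinic dose of trial drug**

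| Visit | Clinic dose | Could follow a home dose of trial drug that morning? | Named in the withhold rule? |
|---|---|---|---|
| 2 | yes (first dose) | no | not needed |
| 3 | yes | yes | yes |
| 4 | yes | yes | yes |
| 5 | yes | yes | yes |
| 6/EoT | yes (last dose) | yes | **no** |

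Four visits need the rule and three have it.

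**Do the Visit 6 instructions fit together?** Three statements apply on that morning: two puffs at home every morning, a dose in clinic, and one dose a day. All three cannot be followed at once. At Visits 3 to 5 the withhold sentence settles the matter by cancelling the home dose. At Visit 6 nothing readable does so. The text does not order a double dose; it leaves the conflict unresolved.

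**Dose if both are taken** (strength 2.5 µg of each component per actuation, Protocol section 4.1.1)

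- Home 2 + clinic 2 = 4 actuations.
- 4 × 2.5 µg = 10 µg tiotropium, plus 10 µg olodaterol in the combination arm.
- Specified daily dose: 2 × 2.5 µg = 5 µg, or 5/5 µg.
- Ratio: 10 / 5 = 2.

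**Share of the whole course.** Assume a fully adherent completer whose Visit 6 falls on Day 360: 361 / 360 − 1 = 0.28%. The visit window allows up to 7 days more; at Day 367 the figure is 368 / 367 − 1 = 0.27%.

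**Effect on the analysis.** SAP section 6.1 ends the actual treatment period 1 day after the last intake, and SAP section 7.7 computes exposure from the drug start and stop dates. A second dose on the same date moves neither. Section 6.2.3.1 lists vital signs and laboratory tests ahead of the last drug administration but does not fix the order, so the documents show no bias in the Visit 6 safety data.

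**With Visit 6/EoT added to the rule.** Clinic dose only: 2 × 2.5 µg = 5 µg of each component, which matches the regimen.

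**The case against.** The best case for leaving the text alone has four parts.

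- **Once daily already answers it.** The regimen is stated repeatedly, including in the patient leaflet, and Visit 6 has its own sentence placing the last dose in clinic. The home and clinic paragraphs can be read as two settings for one daily dose. A careful site would probably reach that reading. But the same inference was open at Visits 3 to 5, and the sponsor still gave an explicit instruction there. The Visit 6 sentence says where the final dose is taken; it does not say to skip the morning one.
- **Visit 6 differs because no new inhaler is assigned.** At Visits 3 to 5 two devices are in play, which may explain the wording. It explains which device is used, not why a home dose would be harmless. The patient has the current inhaler at home that morning, and section 4.1.6 says it locks only after 60 actuations, so it would not stop a second dose unless nearly empty.
- **The instruction may exist elsewhere.** Some appointment text for Visits 2 to 6 is garbled or redacted, and the Investigator Site File and reminder card are not available. This stands as a limit: the documents show that section 4.1.4.2 is incomplete, not that patients were never told. The damaged lines do appear to deal with scheduling.
- **The consequence is trivial.** Much of this stands. The documents show no harm from one doubled dose and no effect on efficacy, and the point about early discontinuers covers only those still taking drug on the morning of the EoT visit. That limits the weight of the point but does not make the list complete.

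**Conclusion.** The point holds. The withhold rule misses its own purpose at one of the four visits where it applies, and no readable text closes the gap.

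The size is small: at most one extra dose per patient, on the last treatment day, giving 10/10 µg or 10 µg against 5/5 µg or 5 µg. It can arise for any patient who reaches Visit 6, or an early EoT visit, while still taking drug, in a trial of about 7800. The documents give no basis for saying how many would take both doses. There is no material effect on the efficacy endpoints, and none on power or the type I error rate.

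The omission from section 4.1.4.2 is certain. Whether patients in practice lacked the instruction depends on site materials that are not available. It should be corrected because it concerns dosing safety and is so easy to put right.

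**What to change.** In Protocol section 4.1.4.2, extend the list of visits in the withhold sentence to 3, 4, 5 and 6/EoT. Add a reminder to the Visit 5 appointment entry in section 6.2.2.2. For patients stopping early who are still taking drug, give the same reminder when the EoT visit is arranged.

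The cost is a few words in one sentence and a reminder line. Sample size, timeline and analysis do not change.

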### **Study medication administration at clinic visits**

#### Dispensation and Respimat® inhaler assembling

Trial medication will be dispensed at visits 2, 3, 4 and 5. Patients will receive 3 new Respimat® treatment boxes + 1 Respimat® inhaler reserve. If the reserve kit is unused and intact, the IRT will not dispense a replacement reserve kit. During the clinic visit only one new Respimat® inhaler should be primed (= cartridge inserted and primed) under the oversight of the site staff. The other Respimat® inhalers should NOT be assembled prior to leaving the clinic.

#### Drug administration

At each clinic visit, oral inhalation of two puffs of the study medication from the new assigned Respimat® inhaler will be self-administered by the patient under the direct supervision of the investigating physician or deputy. The investigator or qualified study personnel will observe the inhalation procedure. For training session please refer to [section 4.1.4.3](#).

### Respimat® inhalers return

At visits 3, 4, 5 and 6 all used and unused Respimat® will be returned to the clinic by the patient. If the reserve kit is unused and intact, the IRT will not dispense a replacement reserve kit.

For rescue medication dispensation, please refer to [section 4.2.1](#)

### **Study medication administration at home**

Each morning, oral inhalation of two puffs on the study medication from the assigned Respimat® inhaler will be self-administered by the patient. Patients should be encouraged to take their study medication at approximately the same time in the morning (morning dose window until noon). If a patient misses the daily dose he/she should take the next dose the day after. The patient must assemble and prime the Respimat® inhaler at home once the current used Respimat® inhaler is empty and the device is locked.

The patient will be asked to record any missed dose of study medication in a patient's reminder card.

#### 4.1.4.3 Inhaler devices training

#### SPECIAL CONSIDERATION:

Most severe to very severe COPD patients are currently using different inhalation medications at the same time. This may cause technical challenges and affect their treatment adherence. Throughout the course of the study treatment period, the correct usage of their inhalation medications should be regularly re-instructed (ideally at each clinic visit) based on the package insert.

#### Respimat®

Training on the use of the Respimat® inhaler will first be provided to the site staff who will subsequently train the patients.

- At visit 1: the first patient's training session will be performed with the intention to familiarise the patient with the Respimat® inhaler training medication (placebo). Detailed written instructions for the use of the Respimat® inhaler will also be given. (See [Appendix 10.1](#)).
- At visit 2: after the randomization, the second patient's training session will be performed from the new assigned Respimat® inhaler. Instructions on how to assemble and prime the Respimat® inhaler at home should also be instructed.
- Subsequent clinic visits: observance of the inhalation procedure. The correct inhalation technique should be reinforced in case of inadequate use of Respimat® inhaler. It is also

**Proprietary confidential information.**

© 2015 Boehringer Ingelheim International GmbH or one or more of its affiliated companies. All rights reserved.

This document may not - in full or in part - be passed on, reproduced, published or otherwise used without prior written permission.

important to remind the patient on how to assemble and prime the Respimat® inhaler at home.

#### Rescue medication

Before using for the first time the Salbutamol (albuterol\*) HFA MDI inhalation aerosol, one actuation should be released into the air to make sure the device is working. The patient's inhaler technique should be reviewed and corrected if needed at each clinic visit.

#### 4.1.4.4 Respimat® malfunctioning

Any Respimat® inhaler that has been reported as malfunctioning by a patient or investigator will be returned to Boehringer Ingelheim for investigation. See the ISF for specific instructions and for details regarding drug accountability requirements.

Details of the procedure for the return of malfunctioning inhalers are provided in [Appendix 10.2](#).

### 4.1.5 Blinding and procedures for unblinding

#### 4.1.5.1 Blinding

Patients, investigators and everyone involved in analysing or with an interest in this double-blind study will remain blinded with regard to the randomised treatment assignments until after database lock.

Boehringer Ingelheim will generate and store the randomisation schedule, and prepare and code the medication in a blinded fashion. Trial supplies will be assigned to the patients via IRT.

Refer to Section 4.1.5.2 for rules of breaking the code in emergency situations.

#### 4.1.5.2 Procedures for emergency unblinding

The ability to unblind will be available to the investigator via the IRT. Unblinding must only be used in emergency situations when the identity of the study drug must be known by the investigator to provide appropriate medical treatment. Each site receives a manual from the IRT provider that contains instructions on how to unblind the treatment of a patient via the IRT (via 24-hour Emergency helpline). If possible, the Clinical Monitor Local (CML) and Trial Clinical Monitor (TCM) must be contacted prior to the site unblinding a patient's treatment. Patients unblinded to treatment will be withdrawn from the trial.

